5.1.3 Displays of Dose-Limiting Toxicities

Analysis Set: DLT Analysis Set

Analysis

Variable(s) : TEAE

Analytical

Method(s): The following summaries will be provided using frequency distribution for each treatment group.

TEAEs considered as dose-limiting toxicities will be coded using the MedDRA and will be summarized using SOC and PT. SOC will be sorted alphabetically and PT will be sorted in decreasing frequency.

 Treatment-Emergent Adverse Events Considered as Dose-Limiting Toxicities by System Organ Class and Preferred Term

The frequency distribution will be provided according to the rules below. Number of subjects

A subject with multiple occurrences of TEAE within a SOC will be counted only once in that SOC. A subject with multiple occurrences of TEAE within a PT will be counted only once in that PT. Percentages will be based on the number of subjects in the DLT analysis set.

5.2 Pretreatment Events

5.2.1 Displays of Pretreatment Events

Analysis Set: All Subjects Who Signed the Informed Consent Form
Analysis
Variable(s): PTE
Analytical
Method(s): The following summaries will be provided using frequency distribution. PTEs will be coded using the MedDRA and will be summarized using SOC and PT. SOC will be sorted alphabetically and PT will be sorted in decreasing frequency.
(1) Pretreatment Events by System Organ Class and Preferred Term
(2) Serious Pretreatment Events by System Organ Class and Preferred Term
Number of subjects

A subject with multiple occurrences of PTE within a SOC will be counted only once in that SOC. A subject with multiple occurrences of

PTE within a PT will be counted only once in that PT.

5.3 Laboratory and Other Safety Data

5.3.1 Laboratory Test Results

5.3.1.1 Hematology, Biochemistry, and Lipid and Glycated Hemoglobin in Blood

Analysis Set: Safety Analysis Set

Analysis

Variable(s): Hematology

	Red Blood Cell	White Blood Cell	Hemoglobin
	Hematocrit	Platelets	
	Differential WBC (Neutrophils, Neutrophil Count, Basophils, Eosinophils,		
	Lymphocytes, Monocytes)		
	Biochemistry		
	Protein Total	Albumin	Glucose
	Creatinine	Blood Urea	Uric Acid
		Nitrogen	
	Bilirubin Total	ALT (GPT)	AST (GOT)
	LDH	GGT	Alkaline Phosphatase
	СК (СРК)	Sodium	Potassium
	Chloride	Calcium	Corrected Calcium
	Phosphorus	PT-INR	
	Lipid and Glycated Hemog	globin in Blood	
	Triglycerides	Total Cholesterol	HDL Cholesterol
	LDL Cholesterol	TSH	HbA1c
Categories:	Intensity [Grade 0, Grade 1, Grade 2, Grade 3, Gra		2, Grade 3, Grade 4]
Visit:	(1) and (2):		
	Hematology, Biochemistry: Baseline, D7, D14, D21, D28, SFU		
	Lipid and Glycated Hemoglobin in Blood: Baseline, D28, SFU		
Analytical			
Method(s) :	For each variable, summaries (1) and (2) will be provided by treatment group. For applicable variables, summaries (3), (4), and (5) will be provided by		
	treatment group. Takeda P	referred SI Units will be us	sed for all summaries.
	(1) Summary of Laborat	ory Test Results and Chang	ge from Baseline by
	Visit		
	Descriptive statistics for observed values and changes from baseline		
	will be provided for	each visit.	
	(2) Case Plots		
		ach subject will be presente	
	(3) Number and Percent	age of Subjects with Elevat	ted Liver Enzyme

Laboratory Parameters

Overall frequency distributions of elevated hepatic parameters will be provided. Further details are given in the Appendix.

(4) Number and Percentage of Subjects with Laboratory Test Abnormalities by Grade

Frequency distributions for each laboratory test abnormality will be provided by grade. Evaluable data (i.e., non-missing and acceptable according to the Handling Rules for Analysis Data) obtained after baseline will be used. A subject with multiple occurrences of laboratory test abnormality will be counted once for the abnormality with the maximum intensity.

(5) Maximum Grade Shift From Baseline of Laboratory Parameters The maximum post-baseline grade will be determined for each subject. Shift tables showing the number of subjects in each grade category at baseline and post-baseline visit will be provided using evaluable data (i.e., non-missing and acceptable according to the Handling Rules for Analysis Data).

5.3.1.2 Urinalysis

Analysis Set:	Safety Analysis Se	t
Analysis		
Variable(s) :	рН	
	Specific Gravity	
	Protein	[-, +-, 1+, 2+, 3+, 4+, 5+]
	Glucose	[-, +-, 1+, 2+, 3+, 4+, 5+]
	Occult blood	[-, +-, 1+, 2+, 3+, 4+, 5+]
	Ketones	[-, +-, 1+, 2+, 3+, 4+, 5+]
	Urobilinogen	[-, +-, 1+, 2+, 3+, 4+, 5+]
	Bilirubin	[-, +-, 1+, 2+, 3+, 4+, 5+]
Categories:	Intensity	[Grade 0, Grade 1, Grade 2, Grade 3, Grade 4]
Visit:	(1), (2), and (3): B	aseline, D7, D14, D21, D28, SFU
Analytical		
Method(s) :	For pH and specifi	c gravity, summaries (1) and (2) will be provided by
	treatment group.	
	For each variable of	other than pH and specific gravity, summary (3) will be
	provided by treatm	ent group.
	For protein, summ	aries (4) and (5) will also be provided by treatment group.

 Summary of Urine Laboratory Test Results and Change from Baseline by Visit

Descriptive statistics for observed values and changes from baseline will be provided for each visit.

- (2) Case PlotsPlots over time for each subject will be presented.
- (3) Number of Subjects in Categories of Urine Laboratory Test Results Shift tables showing the number of subjects in each category at baseline and each post-baseline visit will be provided.
- (4) Number and Percentage of Subjects with Urine Laboratory Test Abnormalities by Grade

Frequency distributions for each urine laboratory test abnormality will be provided by grade. Evaluable data (i.e., non-missing and acceptable according to the Handling Rules for Analysis Data) obtained after baseline will be used. A subject with multiple occurrences of laboratory test abnormality will be counted once for the abnormality with the maximum intensity.

(5) Maximum Grade Shift From Baseline of Urine Laboratory Parameters The maximum post-baseline grade will be determined for each subject. Shift tables showing the number of subjects in each grade category at baseline and post-baseline visit will be provided using evaluable data (i.e., non-missing and acceptable according to the Handling Rules for Analysis Data).

5.3.2 Vital Signs, Physical Findings, and Other Observations Related to Safety

5.3.2.1 Vital Signs and Weight

Analysis Set: Safety Analysis Set Analysis

Variable(s) :	Body Temperature (C)		
	Systolic Blood Pressure (mmHg)		
	Diastolic Blood Pressure (mmHg)		
	Pulse (bpm)		
	Weight (kg)		
Visit:	(1) and (2): Baseline, D7, D14, D21, D28, SFU		
Analytical			
Method(s):	For each variable, summaries (1) and (2) will be provided by treatment group.		
	For applicable variables, summary (3) will be provided by treatment group.		
	(1) Summary of Vital Signs and Weight Parameters and Change from		

50

Baseline by Visit

Descriptive statistics for observed values and changes from baseline will be provided for each visit.

- (2) Case PlotsPlots over time for each subject will be presented.
- (3) Number and Percentage of Subjects with Markedly Abnormal Values of Vital Signs Parameters

Overall frequency distributions of MAV will be provided. If a vital sign parameter has both lower and upper MAV criteria, analysis will be performed for each. Further details are given in Appendix.

5.3.2.2 12-lead ECG

Analysis Set:	Safety Analysis Set		
Analysis			
Variable(s) :	Heart Rate (bpm)		
	RR Interval (msec)		
	PR Interval (msec)		
	QRS Interval (msec)		
	QT Interval (msec)		
	QTcF Interval (msec)	observed value: [Min<= - <=449, 450<= - <=479,	
		480<= - <=499, 500<= - <=Max]	
		change from baseline :	
		[Min<= - <=29, 30<= - <=59, 60<= - <=Max]	
	QTcB Interval (msec)	observed value: [Min<= - <=449, 450<= - <=479,	
		480<= - <=499, 500<= - <=Max]	
		change from baseline :	
		[Min<= - <=29, 30<= - <=59, 60<= - <=Max]	
	12-Lead ECG		
	Interpretation	[Within Normal Limits, Abnormal but not	
		Clinically Significant, Abnormal and Clinically	
		Significant]	
Visit:	(1), (2), and (4): Baseline	e, D14, D28, SFU	
Analytical			
Method(s) :	For each variable other than 12-lead ECG interpretations, summaries (1) and		
	(2) will be provided by treatment group.		
	For applicable variables, summary (3) will be provided by treatment group.		
	For 12-lead ECG interpre-	etation, summary (4) will be provided by treatment	

group.

- (1) Summary of ECG Parameters and Change from Baseline by Visit Descriptive statistics for observed values and changes from baseline will be provided for each visit. Frequency distributions for the categorical variables will be provided for each visit.
- (2) Case PlotsPlots over time for each subject will be presented.
- (3) Number and Percentage of Subjects with Markedly Abnormal Values of ECG Parameters

Overall frequency distributions of MAV will be provided. If an ECG parameter has both lower and upper MAV criteria, analysis will be performed for each. Further details are given in Appendix.

(4) Summary of Shifts of ECG Parameters Shift tables showing the number of subjects in each category at baseline and each post-baseline visit will be provided.

5.4 Displays of Treatment-Emergent Adverse Events (Japanese)

Analysis Set:	Safety Analysis Set
---------------	---------------------

DLT Analysis Set

Analysis

Variable(s): TEAE

Analytical

- Method(s): The following TEAEs will be summarized in the same way as in section 5.1.2 and section 5.1.3. All SOC and PT will be presented in Japanese.
 - (1) Treatment-Emergent Adverse Events by Preferred Term
 - (2) Drug-Related Treatment-Emergent Adverse Events by Preferred Term
 - (3) Treatment-Emergent Adverse Events with Intensity of Grade 3 or Higher by System Organ Class and Preferred Term
 - (4) Treatment-Emergent Adverse Events Leading to Study Drug Discontinuation by System Organ Class and Preferred Term
 - (5) Serious Treatment-Emergent Adverse Events by System Organ Class and Preferred Term
 - (6) Treatment-Emergent Adverse Events Considered as Dose-Limiting Toxicities by System Organ Class and Preferred Term

6 Safety Analysis (Part B)

In this study, safety will be evaluated as the primary endpoint.

6.1 Treatment-Emergent Adverse Events

Analysis will be performed on TEAEs that occurred in Part B.

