Study Design: 
This study consists of two parts: Part A, a dose-rising phase, and Part B, an expansion phase.
 
In Part A, three to six patients will be enrolled in each cohort. Whether or not the study will proceed to the next cohort or Part B will be determined through assessment of tolerability at the dose in question, based on the incidence of dose-limiting toxicity (DLT) in the evaluation period. TAK-385 will be taken once a day for 28 days at the doses assigned to each cohort. Cohort 1 will receive a loading dose of 320 mg and a maintenance dose of 80 mg, Cohort 2 will receive a loading dose of 320 mg and a maintenance dose of 120 mg, Cohort 3 will receive a loading dose of 320 mg and a maintenance dose of 160 mg, and Cohort 4 will receive a loading dose of 360 mg and a maintenance dose of 120 mg. Patients being switched to a gonadotropin-releasing hormone (GnRH) agonist (eg, leuporelin) or a GnRH antagonist (eg, degarelix) following the completion of TAK-385 treatment in Part A will first pass through a 1-week observation period (except for study withdrawals). Whether or not the study will proceed to Part B will be determined by the study sponsor after consulting the study monitoring committee (SMC) based on a comprehensive evaluation of the tolerability and safety data from Cohort 2 of Part A.
 
In Part B, subjects will be randomized to receive study drug (TAK-385 loading dose of 320 mg and maintenance dose of either 80 mg or 120 mg – equal numbers of subjects will be randomized to 80 mg and 120 mg) once a day orally to evaluate safety. In addition to the safety assessments, efficacy assessments will also be performed according to the study schedule, and study drug will be administered until the discontinuation criteria (Section 7.5) are met for each individual subject. After completing 48 weeks of treatment, subject may, at the discretion of the investigator, and depending on the wishes of the subject, continue receiving study drug (for a maximum of 96 weeks), or they may complete the study and be switched to a GnRH agonist or a GnHR antagonist, starting from the day after the day of the last dose of TAK-385.
 
All subjects who receive study drug will undergo safety follow-up 30 to 40 days after the last dose of TAK-385.
		

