##### Part B

To evaluate the safety of TAK-385 in hormone treatment-naive patients with non-metastatic prostate cancer.

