**Table 6.b Study Schedule (Part B)**

Screening	Treatment Period	Continuation Treatment Period	Safety Follow-up
Outpatient			
Days -28 to -1 *1	Week 1, Day 1 *1 to Week 48, Day 7 *2	Week 49, Day 1 to Week 96, Day 7 *2	30 to 40 days after the last dose of TAK-385
Screening tests Assessment of eligibility, randomization	Tests, observations Treatment initiation Treatment completion	Tests, observations Treatment initiation Treatment completion	Initiation of other treatment Tests, observations

\*1: Day -1 and Day 1 are the day before treatment initiation and the day of treatment initiation, respectively.

\*2: Other treatments may be initiated starting on the day after the day of the last dose of TAK-385 (Week 48, Day 8 or Week 96, Day 8).

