Based on these existing data on TAK-385 and on the development plan, it was decided that the loading dose for Cohort 1 in Part A of this study should be 320 mg, a dose that is within the range of doses that have been confirmed to be safe in single dosing, and that can be reliably expected to suppress serum testosterone levels within 48 hours. Given that TAK-385 is going to be used in patients with prostate cancer, the company concluded that it would be necessary to use a dose that could be expected to be effective from the beginning, and that this dose would be tolerated as the loading dose in Japanese. The maintenance dose was set at 80 mg, which can be expected to suppress serum testosterone levels.

(3) Rationale for dosage in Part A, Cohort 4

320 mg or 360 mg may be selected as the loading dose in the planned phase 3 multinational study. Based on this situation, a new cohort, Cohort 4, was added to Part A in Amendment 2 of the study protocol, designed to evaluate the tolerability of loading dose of 360 mg in Japanese patients before joining the phase 3 multinational study. As for the maintenance dose, the same dose as Part A, Cohort 2 (120 mg) was selected, since this dose is expected to keep serum testosterone at castration levels and maintain this effect.

As described in the section above, the tolerability of single doses of 360 mg and multiple doses as high as 160 mg (for 28 days) has been confirmed in a phase 1 study in healthy adult males that was conducted in Europe (TAK-385 C27001).

 Based on the fact that there are no major differences between Japanese and Americans in the pharmacokinetic or pharmacodynamic profiles of TAK-385, and that there are no major differences between the pharmacokinetic profiles obtained in healthy adult men and women, there are no safety concerns in using the loading dose of 360 mg and maintenance dose of 120 mg in Part A, Cohort 4.

(4) Rationale for endpoints

1) Rationale for the primary endpoints

The endpoint in Part A is DLT, in order to confirm the tolerability of TAK-385 in multiple dosing. AEs, clinical laboratory tests, vital signs, and 12-lead ECGs were also made primary endpoints, in order to confirm safety.

In part B, the primary endpoints were made AEs, clinical laboratory tests, vital signs, and 12-lead ECGs, in order to confirm the safety of the use of TAK-385 in multiple dosing for 48 weeks.

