## 10.2 Procedures

### 10.2.1 Collection and Reporting of Adverse Events

#### 10.2.1.1 Collection Period of Pretreatment Events and Adverse Events

Pretreatment events will be recorded continuously from when informed consent is obtained until the first dose of study drug (Day 1). If it is decided that a subject should be withdrawn before the first dose of study drug, PTEs will be recorded until that point in time.

AEs will be recorded continuously from the start of study drug administration to subjects (Day 1) until the safety follow-up.

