5.3.2 Vital Signs, Physical Findings, and Other Observations Related to Safety	
5.4 Displays of Treatment-Emergent Adverse Events (Japanese)	
6 Safety Analysis (Part B)	53
6.1 Treatment-Emergent Adverse Events	53
6.1.1 Overview of Treatment-Emergent Adverse Events	53
6.1.2 Displays of Treatment-Emergent Adverse Events	54
6.2 Pretreatment Events	56
6.2.1 Displays of Pretreatment Events	56
6.3 Laboratory and Other Safety Data	57
6.3.1 Laboratory Test Results	57
6.3.2 Vital Signs, Physical Findings, and Other Observations Related to Safety	60
6.4 Displays of Treatment-Emergent Adverse Events (Japanese)	62
7 Significance Level and Confidence Coefficient (Part A and Part B)	62
Amendment History	63
Appendix 1. Amendments from the Previous Version	1
Appendix 2. Criteria for Markedly Abnormal Values and Elevated Liver Enzyme	1
Appendix 3. QOL Scoring Procedures	1

Glossary

- Treatment-emergent adverse event (TEAE): An adverse event whose date of onset occurs on or after the start of study drug
- Descriptive statistics: number of subjects, mean, standard deviation (SD), maximum (max), minimum (min), and quartiles
- CV: coefficient of variation
- Randomized set: All subjects who were randomized. The first maintenance dose prescribed will be used as the treatment group when conducting analyses.
- Treatment group: For part A, the assigned cohort will be the treatment group. For part B, the first maintenance dose prescribed will be the treatment group.
- PK: pharmacokinetic
- MAV: markedly abnormal value
- ATC: anatomical therapeutic chemical
- LDH: lactic dehydrogenase
- GGT: gamma-glutamyl transpeptidase
- CK (CPK): creatine phosphokinase/kinase
- Study Day: The day before the first dose of the study drug will be defined as Study Day -1 and the day of the first dose will be defined as Study Day 1. If the date of the observation is on the same date or after the day of the first dose, Study Day will be calculated relative to Study Day 1. Otherwise, Study Day will be calculated relative to Study Day -1.
- Follow-up Day: The day after the last dose of the study drug will be defined as Follow-up Day
 1. Follow-up Day will be calculated relative to Day 1.

Definition of Visit Window

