6.1.2 Displays of Treatment-Emergent Adverse Events

Analysis Set:	Safety Analysis Set	
Analysis		
Variable(s) :	TEAE	
Categories:	Intensity	[Grade 1, Grade 2, Grade 3, Grade 4, Grade 5]
	Time of Onset (day)	[1<= - <=90, 91<= - <=180, 181<= - <=270,
		271<=-<=360, 361<=-<=450, 451<=-<=540,
		541<= - <=630, 631<= - <=Max]

Analytical

Method(s): The following summaries will be provided using frequency distribution for each treatment group.

TEAEs will be coded using the MedDRA and will be summarized using SOC and PT. SOC will be sorted alphabetically and PT will be sorted in decreasing frequency for tables provided by SOC and PT. SOC and PT will be sorted in decreasing frequency for tables provided by System Organ Class only or PT only.

TEAEs will be graded using the National Cancer Institute-Common Terminology Criteria for Adverse Events (CTCAE) Version 4.03.

- Treatment-Emergent Adverse Events by System Organ Class and Preferred Term
- (2) Treatment-Emergent Adverse Events by System Organ Class
- (3) Treatment-Emergent Adverse Events by Preferred Term
- (4) Drug-Related Treatment-Emergent Adverse Events by System Organ Class and Preferred Term
- (5) Drug-Related Treatment-Emergent Adverse Events by Preferred Term
- (6) Intensity of Treatment-Emergent Adverse Events by System Organ Class and Preferred Term

- (7) Intensity of Drug-Related Treatment-Emergent Adverse Events by System Organ Class and Preferred Term
- (8) Treatment-Emergent Adverse Events with Intensity of Grade 3 or Higher by System Organ Class and Preferred Term
- (9) Treatment-Emergent Adverse Events Leading to Study Drug Discontinuation by System Organ Class and Preferred Term
- (10) Serious Treatment-Emergent Adverse Events by System Organ Class and Preferred Term
- (11) Treatment-Emergent Adverse Events by System Organ Class and Preferred Term Over Time
- (12) Special Interest Treatment-Emergent Adverse Events by System Organ Class and Preferred Term

The frequency distribution will be provided according to the rules below. Number of subjects

• Summary tables other than (6), (7), (8), and (11)

A subject with multiple occurrences of TEAE within a SOC will be counted only once in that SOC. A subject with multiple occurrences of TEAE within a PT will be counted only once in that PT. Percentages will be based on the number of subjects in the safety analysis set.

• Summary tables for (6), (7), and (8)

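### Part B TEAE tables run for up to 96 weeks with no 48-week summary, so crude incidence depends in part on who continues treatment

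*SAP*

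**What the plan says.** Protocol 6.2, in the rationale for endpoints, says that the Part B primary endpoints (AEs, laboratory tests, vital signs, ECGs) were set "in order to confirm the safety of the use of TAK-385 in multiple dosing for 48 weeks". The Part B objective in Protocol 5.1.1 is wider: "To evaluate the safety of TAK-385 in hormone treatment-naive patients with non-metastatic prostate cancer". Neither it nor the endpoint list in 5.2.1 gives a duration.

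Table 6.b of the protocol places an optional continuation period, "Week 49, Day 1 to Week 96, Day 7", inside Part B. Entry is at the investigator's discretion and the subject's wish (2.0, 6.1), and 6.2 adds that the investigator or sub-investigator must find no safety problems at 48 weeks.

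On the analysis side, SAP 6.1 says "Analysis will be performed on TEAEs that occurred in Part B". The SAP Glossary defines a TEAE as "An adverse event whose date of onset occurs on or after the start of study drug", with no end to the window. Protocol 10.2.1.1 collects events up to the safety follow-up, 30 to 40 days after the last dose. In SAP 6.1.2, percentages in tables (1) to (10) and (12) are based on the whole safety analysis set. Table (11) splits events by onset in 90-day intervals, including "271<=-<=360, 361<=-<=450, 451<=-<=540", and uses the subjects still at risk as denominator.

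**The concern.** A crude percentage with a fixed denominator is interpretable when everyone is observed for about the same time. Here, subjects who stop at Week 48 contribute about 48 weeks plus follow-up, and continuers contribute up to twice that. The share who continue is not fixed by design. It depends on tolerability, and SAP 2.1.4 itself lists an adverse event among the reasons for not entering the extension.

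The percentage for a dose group therefore reflects both its risk and its continuation rate. Two groups with the same risk can look different. Equally, a less well tolerated dose may have fewer continuers, less follow-up and fewer late events counted, which would hide a real difference. No planned table gives the cumulative incidence over the 48 weeks named in the endpoint rationale. These descriptive percentages belong to the primary result of Part B, so what they estimate should be clear.

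**Working it through.** **The plan's own figure.** Protocol 13.3 states about an 80% chance of seeing an AE of 10% true incidence with 15 subjects per group. Exact binomial: 1 − 0.9^15 = 0.794. It reproduces and is not in dispute, but the 10% carries no time frame. It serves below as the illustrative rate.

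**Where Week 48 falls.** 48 × 7 = Day 336, and the SAP schedules WK49D1 at Day 337. Week 96 ends on Day 672. The interval 271–360 holds 66 days up to Day 336 and 24 days after it, so no row of table (11) closes at 48 weeks.

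**Can table (11) be summed to 48 weeks?** No. Its denominators change from row to row, and a subject with the same term in two intervals counts in both. It is also given only by SOC and PT, not by severity, seriousness or relatedness.

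**Size of the effect (illustration).** Assumptions that are not in the documents: everyone completes 48 weeks; continuers complete 96; the hazard is constant and the same for continuers and others; incidence by Day 336 is 10%; events after the last dose are ignored.

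- Incidence by Day 672: 1 − 0.9² = 0.19.
- Crude group incidence with share f continuing: (1 − f) × 0.10 + f × 0.19 = 0.10 + 0.09f.

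| Continuing | Crude incidence |
|---|---|
| 0/15 | 10.0% |
| 5/15 | 13.0% |
| 10/15 | 16.0% |
| 12/15 | 17.2% |
| 15/15 | 19.0% |

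With 12/15 in one group and 5/15 in the other, the gap is 17.2 − 13.0 = 4.2 points with no difference in risk. The extreme, 15/15 against 0/15, is 9 points.

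**Sensitivity.** Let the hazard after Week 48 be r times the earlier one, so that incidence by Week 96 is 1 − 0.9 × 0.9^r.

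- r = 0.5: 14.6% for a continuer; at 10/15 continuing, 0.10 + 0.046 × 10/15 = 13.1%.
- r = 0.25: 12.3% even if all continue.
- r = 0: 10% whoever continues.
- r = 1 with 40 days of follow-up counted: from 1 − 0.9^(376/336) = 11.1% to 1 − 0.9^(712/336) = 20.0%.

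**In subjects.** One subject in 15 is 6.7 points. A 4.2-point gap is 0.042 × 15 = 0.6 of a subject, and 9 points is 1.35 subjects.

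**With a common Day 336 cut.** Under the same assumptions, expected incidence is 10% in both groups whoever continues, and the detection probability is 79.4%. Without the cut, the detection probability ranges from 79.4% to 1 − 0.81^15 = 95.8%.

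**The case against.** The best defence is that the SAP follows the protocol's analysis section. Protocol 13.1.7 asks for TEAEs by part and dose with no 48-week limit, and the study summary allows an evaluation period of about two years for those who continue. A reader might infer that the SAP contradicts a stated 48-week objective or endpoint. The documents do not support that: the 48-week aim appears only in the rationale, and 5.1.1 and 5.2.1 are silent on duration.

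A reader might also infer that every TEAE table is affected alike. That is wrong too. Table (11) handles unequal follow-up within intervals, and its first three intervals lie wholly inside 48 weeks. Unequal continuation would also be visible, because SAP 2.1.4 reports disposition at 48 and 96 weeks and 2.3.1 reports exposure by group. The by-visit summaries of laboratory tests, vital signs and ECGs have their own WK49D1 row.

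Finally, the documents give no continuation rates and no time course for AEs. Some events may come early: Protocol 4.1.2.5 reports that transaminase abnormalities seemed likelier within two weeks at higher doses. Continuers are selected for having no safety problem, so their later hazard may be lower. No between-dose test is planned.

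All of this stands, and it limits the size and the wording of the point. It does not supply a cumulative 48-week incidence, overall or by severity, seriousness or relatedness.

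**Conclusion.** The point holds as a gap in the analysis: the plan has no TEAE summary for the 48-week period that its own rationale names, and the crude full-period percentages vary with elective, safety-dependent continuation. For an AE with 10% incidence by Week 48, the shift runs from nil to 9 points, or at most about one subject in 15. That range rests on an assumed hazard and assumed continuation shares. It would be too strong to say that a false dose difference of any particular size will appear, since the documents give no inputs for that. The change is worth making because the effect is systematic for late-onset events and the remedy is cheap. It does not call the conduct of the trial into question.

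**What to change.** In SAP 6.1, add the overview and the main TEAE tables restricted to onset from Day 1 through Day 336, that is, before WK49D1. Apply the same cut to every subject. Those who stop early count through their safety follow-up or Day 336, whichever comes first. Without that limit, a subject stopping on Day 330 would be counted to about Day 360 to 370, while a 48-week completer would be cut at Day 336.

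Keep the full-period tables alongside. They retain all serious and fatal events and the follow-up events after Day 336. Preferably add exposure-adjusted rates to them. In table (11), end one onset interval at Day 336, and change the exposure intervals in SAP 2.1.5 and 2.3.1 to match.

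Onset dates are already collected, so no new data and no protocol change are needed. The cost is SAP wording and one repeat of the table programs.
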